3.0 Study Objectives and Endpoints

3.1 Study objectives.

The objectives of the proposed study are:

- 1) To evaluate the feasibility and acceptability of a proactive tobacco treatment referral model for patients who use tobacco after diagnosis with cancer.
- 2) To generate estimates of the reach, effectiveness (in terms of abstinence up to 6 months after a target quit day), efficiency (i.e., cost-effectiveness), and equity of enhanced smoking treatment relative to a lower-intensity standard care comparator.

The primary endpoints in this feasibility pilot will be the reach of smoking treatment among adult patients diagnosed with cancer who continue smoking after diagnosis and 7-day point-prevalence abstinence from smoking 26 weeks after a target day to quit smoking (as a measure of effectiveness). Additional important endpoints include: patient perspectives on smoking treatment outreach and counseling (elicited in qualitative interviews), retention in and completion of treatment activities (as additional measures of feasibility and acceptability), costs and cost-effectiveness (to assess relative efficiency of the two active treatments), and differences in comparative treatment effects across patient subpopulations (to assess equity in treatment outcomes). Given the limited sample size in this pilot CET, these endpoints will be used to generate estimates of effects and sample size needs for a future full-scale CET.

3.2 Primary & Exploratory Aims

Primary Aims

Aim 1: To establish the feasibility of the CET protocol and procedures in preparation for a full-scale future trial.

Aim 2: To generate estimates of the size of the comparative effects of intensive, cancer-specific smoking cessation treatment versus a generic, lower-

PROTOCOL TITLE: Comparative Effectiveness Trial of Tobacco Cessation Treatments among Cancer Patients who Smoke

intensity recommended smoking cessation treatment in terms of biochemically confirmed 7-day point prevalence abstinence (no smoking in the past 7 days) 26 weeks after a target quit date.

Exploratory Aims

Aim 3: To estimate differences in CET arms in exploratory outcomes including patient acceptability, completion, adherence, costs, and cost-effectiveness.

Aim 4. To elicit input from patients who have experienced cancer to inform study methods and interventions.

Aim 5. To estimate the extent to which treatment effects on abstinence and exploratory outcomes differ across patient subpopulations based on demographics (age, race, sex, ethnicity, socioeconomic disadvantage); nicotine dependence; and cancer site, stage, and treatment phase.

Aim 4. To explore relations between 1) engagement in tobacco treatment and 2) quitting smoking and health and healthcare utilization outcomes, including cancer outcomes overall, and as a function of environmental exposures and, for those enrolled in the CET, randomly assigned treatment condition.

3.3 Study hypotheses.

The primary hypothesis to be tested for Aim 1 is that at least 12% of eligible adult patients who have cancer and smoke cigarettes and are referred to the tobacco treatment outreach team will initiate an evidence-based form of smoking treatment (either Wisconsin Tobacco Quit Line care or treatment offered in the CET).

The primary hypothesis to be tested for Aim 2 is that more-intensive, cancer-specific smoking cessation treatment will increase the log odds of achieving 7-day abstinence 26 weeks after a target quit date by at least 50% over the comparator condition (predicted odds ratio ≥ 1.50).

Exploratory hypotheses include the following:

For Aim 3, we hypothesize that the majority of patients assigned to each condition will initiate treatment and will receive at least some counseling and use at least some of the provided medication. We also hypothesize that patient ratings of acceptability and satisfaction will be favorable. We also expect retention, adherence, and satisfaction with treatment to be higher in enhanced care relative to the standard care control condition. We anticipate that the more-intensive treatment, although more costly, will be cost-effective in terms of the incremental cost effectiveness ratio per additional

PROTOCOL TITLE: Comparative Effectiveness Trial of Tobacco Cessation Treatments among Cancer Patients who Smoke

patient who quits smoking, relative to the comparator condition and to other preventive health interventions.

For Aim 4, we are not testing a specific hypothesis. Instead, we are seeking patient input to enhance the acceptability of tobacco treatment outreach and the relevance of smoking cessation counseling for participants in the CET.

For Aim 5, we expect treatment reach to be especially high among historically undertreated populations (including African-American, Medicaid-eligible patients, and those from disadvantaged neighborhoods), and for the effects of enhanced care (vs. the standard care comparator) to be similar across patient subgroups.

3.4 Study endpoints.

Primary endpoints:

1. Reach of smoking treatment, defined as the proportion of eligible patients who initiate evidence-based smoking treatment through the opt-out referral program. (Aim 1)
2. Biochemically verified 7-day point-prevalence abstinence 26 weeks after a target quit date (confirmed by expired carbon monoxide and/or a cotinine urine or saliva sample test). (Aim 2)

Secondary endpoint:

1. Self-reported 7-day point-prevalence abstinence 12 weeks after a target quit date. (Aim 2).

Exploratory endpoints:

1. Treatment acceptability and feasibility indicators including treatment retention (at each treatment contact/milestone) and completion, medication adherence, patient satisfaction, and patient ratings of burden. (Aim 3).
2. Treatment costs from payer and patient perspectives. (Aim 3).
3. Incremental cost-effectiveness ratios for each additional patient who quits smoking with higher-intensity treatment versus lower-intensity treatment. (Aim 4).
4. Differences in rates of treatment reach, retention, and completion by patient factors (demographics, nicotine dependence, smoking history). (Aim 5).
5. Moderation of treatment effects (high- vs. low-intensity) by patient factors. (Aim 5).

PROTOCOL TITLE: Comparative Effectiveness Trial of Tobacco Cessation Treatments among Cancer Patients who Smoke

6. Health outcomes (e.g., cancer mortality, cancer progression, new cancer diagnoses, treatment side effects).

3.5 Primary safety endpoints.

1. Adverse events, by treatment condition.
2. Serious adverse events, by treatment condition.

4.0 Number of Participants

4.1 Total number of participants to be accrued. Up to 82 adult participants will be enrolled in the clinical trial by UW-CTRI staff from UW Carbon Cancer Center clinic referrals over 12-30 months. We will continue enrolling within each clinic until we reach saturation in qualitative data analysis of patient interviews (maximum N=32) and until we reach our target enrollment for the CET (N=50).

4.2 Number of participants needed to complete the research procedures. We anticipate that we will engage 12% of participants in some form of evidence-based treatment, and that 50 will enroll in the proposed comparative effectiveness study while another 50 will opt for the Wisconsin Tobacco Quit Line. As such, we anticipate that we will need to reach out to approximately 833 patients who meet criteria to be included on the quarterly CRDS reports that will guide proactive outreach letters and calls. We anticipate that the remaining 733 participants will either opt-out of smoking treatment outreach, will not be reached by the outreach team, will decline tobacco treatment, will elect to pursue treatment via their primary care provider or other means (e.g., over-the-counter) rather than to use formal treatment, or will not complete the treatment enrollment process for other reasons.

Among the 50 participants who enroll in the CET, we will use an intent-to-treat approach to data analyses so that all randomized participants will be included in key analyses of feasibility, acceptability, and abstinence rates, even if lost to follow-up. In primary analyses of abstinence outcomes, missing cases will be treated as still smoking. This will be supplemented by sensitivity analyses under varying assumptions regarding censored data (i.e., that 5%, 10%, or 20% of missing data are abstinent).

For the qualitative interviews, even 2-5 interviews could inform and enhance study methods. We anticipate that we could reach thematic saturation in qualitative data coding with fewer than 32 interviews, and have set 32 as an upper limit for recruitment.

4.3 **Criteria for considering participants “enrolled.”** Individuals will be considered enrolled in the study at the point of randomization to a study arm in the CET. Randomization will occur after oral consent to participate and completion of baseline assessments. People who do not complete oral consent and randomization will not be considered fully enrolled and will be replaced until 50 people are randomized in the CET (25 in each arm).

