In this pilot study, we seek to demonstrate the feasibility and acceptability of the proactive outreach model as a way to enhance the reach of smoking treatment, and as a feasible way to recruit participants for a CET of enhanced vs. standard smoking cessation treatment. We also hope to generate estimates of enhanced vs. standard treatment effects on biochemically verified 7-day point-prevalence abstinence rates 6 months after a target quit date (primary outcome) and other abstinence measures (e.g., self-reported prolonged and point-prevalence abstinence 3 and 6 months post-quit). As such, we selected a sample size of 50 to generate stable estimates of the size of treatment effects on these outcomes and costs,

PROTOCOL TITLE: Comparative Effectiveness Trial of Tobacco Cessation Treatments among Cancer Patients who Smoke

and to permit exploration of differences in treatment effects by sex, race, ethnicity, and disadvantage. A sample of 50, while too small to sensitively test for moderate treatment benefits, is sufficient to pilot test all study and treatment procedures and to yield informative effect estimates that will guide a future, full-scale CET of standard and enhanced care.

The primary outcome will be analyzed in an intent-to-treat analysis in which all randomized participants are included, and missing cases are assumed to be non-abstinent. This will be supplemented by sensitivity analyses that again use the full sample of randomized participants to examine robustness of results across different assumptions regarding missingness. Multiple imputation will not be used in this pilot project.

For the qualitative study, we will recruit as many participants as we can until we reach thematic saturation in qualitative data coding. We anticipate that this will occur with fewer than 32 participants.

20.3 Participant Population(s) for Analysis.

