We will examine reach of the treatment by computing the proportion of all participants meeting inclusion criteria for proactive tobacco outreach who were referred to WTQL, referred to their PCP, and the proportion who were screened for, eligible for, and enrolled/randomized in the CET. As such, the pool of participants for Aim 1 includes everyone eligible for inclusion on at least 1 CRDS report that guides proactive tobacco treatment outreach. The pool of participants included in Aims 2, 3 and 5 will comprise all participants who were randomized to treatment in the CET. The pool for Aim 4 will include all participants who participated in a qualitative interview.

20.4 Statistical Methods.

Descriptive statistics will be used to characterize smoking treatment reach (the proportion of eligible patients who initiate any smoking cessation treatment, and the proportion who enroll in the CET. These rates will be computed overall, and by patient subpopulation.

Logistic regression will be used to estimate the effects of treatment condition on binary outcome data (e.g., abstinence, side effects), overall and by patient subgroups (i.e., moderation effects). Odds ratios and numbers needed to treat will be computed to estimate treatment effect sizes.

Analyses of variance will be used to examine condition effects on continuous variables such as ratings of treatment satisfaction, burden, and treatment effects on ratings of patient experiences and candidate treatment mediators (e.g., withdrawal). Treatment effect sizes will be computed. Cost-effectiveness will be calculated based on the incremental cost-effectiveness

PROTOCOL TITLE: Comparative Effectiveness Trial of Tobacco Cessation Treatments among Cancer Patients who Smoke

ratio of enhanced treatment versus standard treatment per each additional case of abstinence.

Thematic analysis of qualitative interview will identify themes that emerge in patient interviews in the following areas: cancer experiences, supportive care outreach, tobacco history, and tobacco treatment.

20.5 Planned Interim Analysis.

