No formal inferential interim analyses are planned for this pilot study, but safety data will be examined on an on-going basis to determine if individual participants are at risk or if any treatment element or condition is exerting an iatrogenic effect. If any meaningful evidence of this is detected the DSMC will be consulted along with the IRB to consider study discontinuation or changes. If any danger is deemed likely and significant the study will be immediately suspended.

20.6 Handling of Missing Data. The intent-to-treat principle will be applied to primary analyses. Patients who do not initiate smoking treatment via a UW-CTRI study coordinator will be assumed to not have initiated treatment. In analyses of abstinence, cases who do not report abstinence and provide biochemical evidence of abstinence will be coded as still smoking in primary analyses. This will be supplemented by sensitivity analyses to estimate treatment effects under different assumptions regarding missing data (e.g., if 10%, 20% or 30% of people without verified abstinence are abstinent).

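### Satisfaction and burden ratings cannot be analysed in all randomised participants as promised: the planned ANOVA has no rule for missing ratings and is in effect respondents-only

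*Combined protocol and SAP*

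**What the plan says.** **Who is to be analysed.** Section 4.2 adopts an intent-to-treat approach for the 50 randomised participants and says that "all randomized participants will be included in key analyses of feasibility, acceptability, and abstinence rates, even if lost to follow-up". Section 20.3 repeats this by aim: "The pool of participants included in Aims 2, 3 and 5 will comprise all participants who were randomized to treatment in the CET".

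**What counts as acceptability.** The first exploratory endpoint in section 3.4 (Aim 3) covers retention and completion, and also "medication adherence, patient satisfaction, and patient ratings of burden".

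**How the ratings are analysed.** Section 20.4: "Analyses of variance will be used to examine condition effects on continuous variables such as ratings of treatment satisfaction, burden". It names no visit and does not say whether the visits are analysed jointly.

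**When they are collected.** Satisfaction is self-reported at the follow-up calls 12 and 26 weeks after the target quit date (13.1 and the schedule in 13.2). The schedule has no row labelled burden.

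**Missing data.** Section 20.6 gives two rules. One is for treatment initiation: "Patients who do not initiate smoking treatment via a UW-CTRI study coordinator will be assumed to not have initiated treatment". The other is for abstinence: "cases who do not report abstinence and provide biochemical evidence of abstinence will be coded as still smoking in primary analyses". The sensitivity analyses in 4.2, 20.2 and 20.6 are attached to abstinence. Section 20.2 adds: "Multiple imputation will not be used in this pilot project".

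**The concern.** Coding missing as smoking lets the abstinence analysis keep everyone randomised. Nothing comparable exists for a rating. An ANOVA cannot use a person without an outcome value, so anyone lost before week 12 drops out of the satisfaction comparison, despite 4.2 and 20.3.

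If people who dislike their treatment are harder to reach, respondents are more satisfied than the randomised group, and the arm that loses more of them looks better than it is. Different loss by arm is foreseeable. Section 20.1 predicts higher retention in enhanced care. That arm has seven counselling calls against three, and standard care has no counselling call after week 1 (11.1). The contrast would then mix acceptability with retention, and section 3.1 says these endpoints will feed the design of a full-scale trial.

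**Working it through.** The plan states no dropout rate, rating SD or power for these endpoints, so there is no figure of its own to reproduce. The check has two parts.

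**1. Can the promise be kept, indicator by indicator?**

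| Indicator (3.4) | Source | Known if lost to follow-up? |
|---|---|---|
| Retention, completion | Session completion logged in REDCap (13.4) | Yes |
| Adherence, from refills and dispensing | Logged in REDCap (13.4) | Yes |
| Satisfaction | Week-12 and week-26 calls (13.1, 13.2) | No |
| Burden | Patient rating, timing not shown in 13.2 | No, if the rating call is missed |

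The promise fails for the last two rows only, and one participant without a rating is enough for it to fail.

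**2. How large could the bias be?**

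Inputs: 25 per arm (4.3). Assumed: 16% loss in one arm (4 of 25, leaving 21) and 36% in the other (9 of 25, leaving 16). The higher loss is placed in standard care (SC), to follow the plan's expectation of better retention in enhanced care (EC).

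*Simple formula.* Let d be the fraction lost in an arm, and let those lost score g SD below respondents. The respondent mean then exceeds the all-randomised mean by d × g. With no true difference and the same g in both arms, the false EC − SC contrast is g × (d_EC − d_SC):
- g = 0.5: 0.5 × (0.16 − 0.36) = −0.10 SD
- g = 1.0: 1.0 × (0.16 − 0.36) = −0.20 SD
- Loss rates swapped between arms: +0.10 to +0.20 SD
- Equal loss d with the same g: zero. With g = 1.0 in EC and 0.5 in SC, the bias is d × 0.5, so 0.10 SD at 20% loss.

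*Simulation.* No true difference, week-12/week-26 correlation 0.6, log-odds slope of loss 1 to 2 per SD, 1,000,000 per arm. The table gives the absolute size of the false week-26 difference:

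| What drives loss | Respondents only | Likelihood model, both visits |
|---|---|---|
| Observed week-12 rating, lost after week 12 | 0.10 to 0.14 SD | under 0.01 SD |
| Unseen week-26 rating, lost after week 12 | 0.16 to 0.23 SD | 0.11 to 0.17 SD |
| Lost before week 12, no rating at all | 0.10 to 0.14 SD | nothing to recover it from |

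*Extreme case.* If exactly the least satisfied are lost, the respondent mean in an arm is φ(z_d)/(1 − d). That is 0.290 SD at 16% and 0.585 SD at 36%, a false difference of 0.295 SD.

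*Precision.* The 95% half-width is 1.96 × √(1/n_SC + 1/n_EC):
- 25 and 25: 0.55 SD
- 16 and 21: 1.96 × √(0.0625 + 0.0476) = 0.65 SD

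A bias of 0.10 to 0.20 SD is therefore about 15% to 31% of the half-width.

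**The case against.** **Most of the acceptability promise can be kept.** Section 3.1 itself names retention and completion as measures of feasibility and acceptability, and both are known for everyone. This stands. A reader might infer that the acceptability analysis as a whole fails; the documents support that only for the ratings.

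**The ANOVA need not discard week-12 data.** A reader might infer that a single-visit analysis throws away the week-12 rating of anyone lost by week 26. Section 20.4 does not say so. Separate ANOVAs at each visit fit the text equally well, and where everyone answers at week 12, a week-12 ANOVA is unbiased. This stands.

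**A mixed model is not a cure.** It removes the bias only when loss depends on a rating already observed. If people stop answering because of how they feel later, or leave before week 12, the bias largely or wholly remains. This stands, and limits what the fix can claim.

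**The bias need not flatter enhanced care.** A reader might suppose that it favours the arm hypothesised to do better. The plan's own retention forecast points the other way. This stands.

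**Materiality is low.** These are exploratory endpoints in a 50-person pilot, the loss rates are assumed, and the bias is small beside the sampling error. Section 20.6 ties intent-to-treat to the primary analyses and nothing labels the ANOVA itself as intent-to-treat. This lowers the weight of the point. It does not remove the conflict, because 4.2 extends the all-randomised statement to acceptability by name and 20.3 extends it to Aim 3.

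**Conclusion.** The point holds for the satisfaction and burden ratings only. Sections 4.2 and 20.3 promise an analysis set that 20.4, with no missing-rating rule and no multiple imputation, cannot deliver. That the ANOVA is complete-case is an inference, but no other handling is described.

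The failed promise needs only one missing rating. Bias is possible rather than certain: it requires that loss, or the gap between responders and non-responders, differs by arm. Under the assumed loss rates and gaps it is about 0.1 to 0.2 SD in either direction, more likely against enhanced care, and well inside a 95% half-width of about 0.65 SD. The loss rates, gap, slope and correlation are all assumptions. The primary abstinence analysis has its own rule and is not touched. This is a worthwhile, inexpensive correction to an exploratory analysis, not a threat to the trial's main result.

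**What to change.** 1. In 4.2 and 20.3, state that satisfaction and burden are analysed among participants with at least one rating, and that the number with none will be reported by arm. Keep the all-randomised statement for retention, completion and dispensing-based adherence.
2. In 20.4, for ratings collected at both weeks 12 and 26, replace the ANOVA with a likelihood-based repeated-measures model (arm, visit, arm-by-visit). It uses everyone with at least one rating and respects the decision against multiple imputation.
3. Confirm when burden is measured and show it in 13.2. If it is rated only once, the joint model does not apply to it.
4. In 20.6, add a sensitivity bound for those with no rating, for example lowest rank in a rank test. Present it as a bound, not a correction.
5. Say plainly that the model corrects only loss explained by observed ratings and does not recover people lost before week 12.

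Cost: a few sentences, a few lines of code and slightly more analysis work, with no new data or visits. The stated analysis set for these ratings becomes less favourable than all randomised.

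### The missing-data sensitivity analysis is stated twice with different fractions and denominators, and neither version names arm-specific scenarios, so it may not show where the abstinence estimate changes direction

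*Combined protocol and SAP*

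**What the plan says.** The comparison is small: people who do not complete consent and randomization "will be replaced until 50 people are randomized in the CET (25 in each arm"). All randomized participants are analysed, "even if lost to follow-up" (section 4.2). For the primary analysis, section 20.6 sets the rule that "cases who do not report abstinence and provide biochemical evidence of abstinence will be coded as still smoking in primary analyses".

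The check on that rule appears in three places:

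- Section 4.2: "sensitivity analyses under varying assumptions regarding censored data (i.e., that 5%, 10%, or 20% of missing data are abstinent"). The base is missing data, and the list is introduced as definitive.
- Section 20.6: "if 10%, 20% or 30% of people without verified abstinence are abstinent". The base is everyone without verified abstinence, and the list is introduced as an example.
- Section 20.2: the sensitivity analyses are to "examine robustness of results across different assumptions regarding missingness". The same paragraph adds: "Multiple imputation will not be used in this pilot project".

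No section names an arm-specific, worst-case or tipping-point scenario. No section gives an expected loss to follow-up.

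**The concern.** Coding missing as smoking can turn a difference in follow-up between arms into an apparent treatment effect. The sensitivity analysis is the only stated protection, because imputation is excluded. For that purpose it has to vary two things: how many outcomes are missing in each arm, and how often the missing people in each arm are in fact abstinent.

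Unequal loss is plausible here. Under section 11.1, scheduled counseling runs to week 12 after the quit date in enhanced care and to week 1 in standard care. Section 3.3 adds: "We also expect retention, adherence, and satisfaction with treatment to be higher in enhanced care relative to the standard care control condition". Verification also needs a visit or a mailed saliva kit (section 13.3), which is a further route to an unverified outcome.

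Section 3.1 says the pilot's estimates will inform the size of a full-scale trial. An effect that looks stable only because the grid is narrow, or on the wrong base, would carry into that design.

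**Working it through.** **Inputs.** 25 per arm (section 4.3); the two sets of fractions (sections 4.2 and 20.6). The plan gives no loss rate and no figure for this analysis that could be reproduced, so the counts below are assumptions: 7/25 verified abstinent in enhanced care (E) and 5/25 in standard care (S). The primary odds ratio (OR) is 7×20/(18×5) = 1.56, near the hypothesized 1.50, and the risk difference (RD) is 2/25 = 0.08.

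**Section 20.6, common fraction f.** Each rate p becomes p + f(1 − p), so the new RD is (1 − f)(pE − pS). The numbers missing do not enter. At 10/20/30% the RD is 0.072/0.064/0.056, whatever the split of missing cases, and the sign cannot change.

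**Section 4.2, common fraction f.** With mE and mS missing, the new RD is 0.08 + f(mE − mS)/25.

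- Equal loss (5 and 5): the RD stays 0.08 for every f; the OR is 1.54, 1.52, 1.49.
- Unequal loss (3 and 8): the RD is 0.08 − 0.2f, which reaches zero only at f = 40%, outside both planned grids.

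**Results for 3 (E) and 8 (S) missing**

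| Scenario | Abstinent E, S | RD | OR |
|---|---|---|---|
| Primary | 7, 5 | 0.08 | 1.56 |
| 4.2 at 5% | 7.15, 5.4 | 0.07 | 1.45 |
| 4.2 at 10% | 7.3, 5.8 | 0.06 | 1.37 |
| 4.2 at 20% | 7.6, 6.6 | 0.04 | 1.22 |
| 20.6 at 10% | 8.8, 7 | 0.072 | 1.40 |
| 20.6 at 20% | 10.6, 9 | 0.064 | 1.31 |
| 20.6 at 30% | 12.4, 11 | 0.056 | 1.25 |
| Missing have own arm's observed rate | 7/22, 5/17 | 0.024 | 1.12 |
| 0 of 3 and 3 of 8 abstinent | 7, 8 | −0.04 | 0.83 |

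The own-arm row is 7×12/(15×5) = 84/75 = 1.12; the last is 7×17/(18×8) = 119/144 = 0.83. With none of the 3 abstinent, the effect is null at 2 of 8 (25%) in standard care. All (3+1)×(8+1) = 36 possible outcomes run from OR 0.36 (7 vs 13 abstinent: 7×12/(18×13)) to 2.67 (10 vs 5: 10×20/(15×5)).

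**The 20% ceiling.** The observed rates here are 7/22 = 32% and 5/17 = 29%; with 5 missing per arm they would be 7/20 = 35% and 5/20 = 25%. All exceed 20%. So do both rates in the cancer trial described in section 2.5 (34.5% and 21.5%). At such rates the 4.2 grid never reaches the case where missing people resemble observed people.

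**If fractions may differ by arm.** The least favourable use of the 4.2 grid (E 5%, S 20%) gives 7.15 and 6.6 abstinent, OR 1.12. The same use of the 20.6 values (E 10%, S 30%) gives 8.8 and 11, OR 0.69. Which section is followed then decides the direction.

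**The case against.** Several stronger readings are tempting, and the documents do not support them.

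- *That the plan applies one fraction to both arms.* It is silent on arms. A common fraction is the natural reading, but section 20.6 gives only examples and section 20.2 is open-ended.
- *That the grid moves about one person or fewer.* For section 4.2 this is true with up to 5 missing per arm (0.25, 0.5, 1.0), but at 20% it is 2 people with 10 missing and 3 with 15. Under section 20.6 the example moves 1.8 to 5.4 people in enhanced care and 2 to 6 in standard care.
- *That it cannot show any effect of unequal loss, or returns almost the same odds ratio every time.* With 3 and 8 missing, the 4.2 grid takes the OR from 1.56 to 1.22, and the 20.6 version takes it to 1.25.

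Unequal loss at week 26 is also not forecast. Both arms have the same 12- and 26-week calls (section 13.2), payment does not depend on arm (section 7.5), and the retention endpoint in section 3.4 concerns treatment contacts. This stands: unequal loss is a possibility, not an expectation.

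Finally, this is an estimation pilot that section 20.2 calls too small to test moderate benefits sensitively. In the example the Wald 95% interval for the OR is 0.42 to 5.78, wider on the log scale than the full range over the missing cases, and the reversal to 0.83 is a chosen scenario. That limits the consequence. It does not remove it: the sampling interval does not cover bias from missing outcomes, and the own-arm scenario, which is not extreme, already falls outside the 4.2 grid.

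**Conclusion.** The concern holds in a limited form. Three parts rest on the text and algebra alone: the two sections conflict on fractions and base; neither names arm-specific scenarios; and at a common fraction the 20.6 version only shrinks the risk difference by (1 − f). Its base also includes people who reported smoking, so it is not purely a missing-data assumption. The 4.2 version does answer to unequal numbers missing; what it leaves out is different abstinence among the missing in each arm, and rates above 20%.

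The size is illustrative. With 7/25 vs 5/25 and 3 vs 8 missing, all assumed, the 4.2 grid stops at OR 1.22, while own-arm rates give 1.12 and one arm-specific outcome gives 0.83. Other loss patterns would give other figures. The importance is moderate: no confirmatory conclusion depends on it, but the estimate is intended for planning a larger trial.

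**What to change.** 1. Reconcile sections 4.2 and 20.6 on one base: participants whose week-26 outcome is missing or unverified, excluding those who reported smoking. State how a reported abstinence contradicted by the test is classed.
2. Report the number missing or unverified in each arm beside the primary result.
3. Replace the percentage grid with an arm-specific tipping-point table: OR and risk difference for every combination of 0 to m1 abstinent among the m1 missing in enhanced care and 0 to m0 among the m0 missing in standard care. Mark where the direction changes, and where the missing have their own arm's observed rate.

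The cost is revised wording and a few lines of code; the example needs 36 two-by-two tables. No new data are required, and the primary analysis and the exclusion of multiple imputation can stay. The downside is that the displayed range will be wider than the present grid would show.
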